9.2.3. Per-Protocol Analysis Set

The per-protocol (PP) analysis set is a subset of the ITT analysis set including only patients without major protocol violations and who have >80% compliance to the IMP over the entire treatment period. Treatment compliance during the study will be assessed based on both data collected in the IMP dose counter and diary. Details will be provided in the SAP. Major protocol violations will be determined before unblinding. Note that since the use of incorrect IMP will be considered a major protocol violation, for treatment assignment in the PP analysis set, “as randomized” will coincide with “as treated.”

The PP analysis set will serve as the supportive population for the primary efficacy analysis only.

9.3. Data Handling Conventions

Data imputation rules will be described in the statistical analysis plan, as appropriate for each endpoint.

9.4. Study Population

The ITT analysis set (Section 9.2.1) will be used for all study population summaries unless otherwise specified. Summaries will be presented by treatment group and for all patients.

9.4.1. Patient Disposition

The following data will be summarized using descriptive statistics: patients screened; patients screened but not enrolled (and reason); patients enrolled in the run-in period; patients enrolled in the run-in period but not randomized (and reason); patients randomized; patients randomized but not treated; patients in the ITT, safety, and PP analysis sets; patients who complete the study; and patients who withdraw from the treatment period of the study and the reason for withdrawal.

9.4.2. Demographic and Baseline Characteristics

Patient demographic and baseline characteristics, including medical history, and prior medications and therapies will be examined to assess the comparability of the treatment groups and will be summarized using descriptive statistics. For continuous variables, descriptive statistics (number [n], mean, SD, median, minimum, and maximum) will be provided. For categorical variables, patient counts and percentages will be provided. Categories for missing data will be presented if necessary.

Patient demographics will be presented for all 3 analysis sets defined in Section 9.2.

9.5. Efficacy Analysis

9.5.1. Primary Endpoint

The primary efficacy endpoints are as follows:

- For Fp MDPI versus placebo: the change from baseline in weekly average of the percent predicted trough morning FEV₁ at week 12
- For FS MDPI versus Fp MDPI: the change from baseline in 1-hour postdose percent predicted morning FEV₁ at week 12

9.5.2. Secondary Endpoints

The secondary efficacy endpoints are as follows:

- Change from baseline in the weekly average of daily trough morning (predose and pre-rescue bronchodilator) PEF over the 12-week treatment period
- Change from baseline in the weekly average of total daily (24-hour) use of albuterol/salbutamol inhalation aerosol (number of inhalations) over weeks 1 through 12

- Change from baseline in the weekly average of the total daily asthma symptom score (defined as the average of the daytime and nighttime scores) over weeks 1 through 12
- Change from baseline in asthma control (measured by C-ACT) score over the 12-week treatment period
- Time to first onset of effect defined as the first decrease from baseline in daily rescue medication use
- Proportion of patients who discontinued from IMP for asthma exacerbation during the 12-week treatment period

The sequential order of the secondary endpoints for multiplicity will be described in the statistical analysis plan.

9.5.3. Other Efficacy Endpoints

The other efficacy endpoints include the following:

- Change from baseline in the weekly average of total daily (24-hour) use of albuterol/salbutamol inhalation aerosol (number of inhalations) at weeks 4, 8, and 12
- Change from baseline in the percentage of rescue-free days (defined as 24-hour periods with no rescue medication usage) during the 12-week treatment period
- Change from baseline in the percentage of symptom-free days (defined as 24-hour periods with asthma symptom score of 0) during the 12-week treatment period
- Change from baseline in the percentage of asthma-control days (defined as 24-hour periods with asthma symptom score of 0 and no rescue medication usage) during the 12-week treatment period
- Change from baseline in 1-hour postdose percent predicted morning FEV₁ at week 1
- Change from baseline in the weekly average of daily evening PEF over the 12-week treatment period
- Change from baseline in weekly average of the percent predicted trough morning FEV₁ at weeks 1, 2, 4, and 8
- Proportion of patients who achieve at least a 15% increase in morning FEV₁ at 1-hour postdose at day 1 (the RV/TV1), week 1, and week 12
- Change from baseline in asthma control (measured by C-ACT) score at weeks 4, 8, and 12
- Time to consistent onset of effect defined as the decrease from baseline in daily rescue medication use on 3 consecutive days

9.5.4. Planned Method of Analysis

The ITT analysis set (Section 9.2.1) will be the primary analysis set to be used for all efficacy analyses. The PP analysis set will serve as the sensitivity analysis set for primary efficacy analyses only. Details will be provided in the statistical analysis plan. Subgroup (sex, age group,

previous therapy [ICS or NCS], and race) analyses will be provided for the primary efficacy endpoints.

9.5.4.1. Primary Estimands and Efficacy Analysis

The specific estimands selected for the 2 primary endpoints will assess the change from baseline due to the initially randomized treatment as actually taken. These estimands assess the effectiveness at week 12, focusing on the causal effects attributable to the initially randomized medication. The sponsor will make all efforts to avoid study withdrawal in this 12-week study. In instances where a patient decides to discontinue IMP or, more importantly, requires alternative therapy for worsening asthma or an asthma exacerbation, the investigators will be instructed to encourage the patient to continue in the study and return for planned visits in order to collect data after IMP discontinuation.

The question of whether to use data collected after IMP discontinuation is an ongoing debate in statistical literature, in particular for studies with symptomatic endpoints and when it is common for patients who dropout to switch therapies (Little and Kang 2015, Mallinckrodt et al 2016, Mallinckrodt 2013, O’Neill and Temple 2012). This study is designed as a placebo-controlled study and it is expected that patients randomized to placebo would discontinue IMP due to worsening asthma at a higher rate than those randomized to active treatment, which is known to be an efficacious drug as established by multiple studies. After a patient discontinues IMP due to worsening asthma, the patient will be placed on alternative asthma therapies, such as systemic corticosteroids, additional medications containing ICS, or both, which would alter the spirometry collected after that point and therefore not be appropriate for assessment of IMP effectiveness. Improvement of asthma would be expected as rapidly and early as 1 week for FEV₁ for placebo patients placed on ICS (Szeffler et al 1999). It has also been shown that patients placed on ICS with long acting beta-agonists can have significant improvement in serial FEV₁ measurements on the same day (Corren et al 2007, Pearlman et al 1999). Therefore, any patient who discontinued IMP and was placed on alternative therapies would be expected to have rapid and demonstrable improvements in lung function approximating or exceeding the levels measured at screening.

The inclusion of patients who failed therapy and who were then treated with alternative medication would blunt the treatment effect, potentially causing the study to fail due to the analysis rather than the effectiveness of the treatment given during the study. These patients no longer represent a true placebo population and including them in the population for the primary outcome is not consistent with treatment by placebo. In light of this, retrieved dropout data will be used only for sensitivity analyses. Missing data for patients who discontinue IMP will be imputed using reference-based multiple imputations representing a missing not at random (MNAR) mechanism. This approach is discussed in Mallinckrodt et al 2016 (Sections 3.2 and 3.4 for estimand 2 in the paper).

Analysis of the change from baseline in weekly average of the percent predicted trough morning FEV₁ at week 12

The baseline percent predicted FEV₁ will be the weekly average of the morning FEV₁ prior to the first IMP dose. The first day before randomization consists of the entry on the morning of the RV in the patient diary built into the handheld device. The weekly average of the percent predicted FEV₁ at week 12 will be the average values based on the available data at that week.

The primary analysis of the change from baseline in weekly average of percent predicted morning FEV₁ at week 12 due to the initially randomized treatment as actually taken will be analyzed using an analysis of covariance (ANCOVA) model with effects due to baseline percent predicted trough morning FEV₁, sex, age, (pooled) investigational center, previous therapy (ICS or NCS), and IMP treatment group. Contrasts for pairwise treatment comparisons of interest will be constructed. The estimated treatment difference between each IMP treatment group and the placebo group will be presented together with the 2-sided 95% confidence interval (CI) for the difference and the p-value.

In this analysis, missing data that are caused by early dropouts from the study or from IMP (regardless of availability of retrieved dropout data) will be imputed using reference-based multiple imputations. Details on the implementation of the multiple imputations will be provided in the statistical analysis plan.

Analysis of the change from baseline in 1-hour postdose percent predicted morning FEV₁ at week 12

For the endpoint of change from baseline in 1-hour postdose percent predicted morning FEV₁ (measured at the clinic) at week 12, baseline is defined as predose FEV₁ measurements obtained at the clinic at the RV with the handheld device immediately prior to the IMP administration.

The primary analysis of the change from baseline in 1-hour postdose percent predicted morning FEV₁ at week 12 due to the initially randomized treatment as actually taken will be analyzed using an ANCOVA model with effects due to baseline percent predicted trough morning FEV₁, sex, age, (pooled) investigational center, previous therapy (ICS or NCS), and IMP treatment group. Contrasts for pairwise treatment comparisons of interest will be constructed. The estimated treatment difference between each IMP treatment group and the placebo group will be presented together with the 2-sided 95% CI for the difference and the p-value. Missing data caused by early dropouts will be handled similarly to the above analysis.

9.5.4.2. Sensitivity Analysis to Missing Data

To assess the impact of missing data, several sensitivity analyses will be conducted for the 2 endpoints by evaluating alternative estimands. More details will be provided in the statistical analysis plan.

- The primary analysis for the 2 endpoints will be repeated when using data collected after IMP discontinuation (retrieved dropout data). Reference-based imputation will be used only for patients with no retrieved dropout data. This analysis estimates different estimands, namely the change from baseline as actually taken (see estimand 1 in [Mallinckrodt et al 2016](#)).
- The primary analysis for the 2 endpoints will be repeated on completers with no major protocol violations (see estimand 3 in [Mallinckrodt et al 2016](#)).
- A tipping point analysis will be performed as a sensitivity analysis to missing data by utilizing multiple imputations under different missing mechanism. For placebo patients, in all applications of multiple imputations, missing at random (MAR) will be assumed. For the active arms, in the first application, MAR will be assumed and the imputations will be drawn from data in the corresponding active arms. In subsequent applications,

shifts to the distribution of the active arms will be applied to represent different degrees of effect loss, ie, MNAR will be assumed. This analysis will utilize only data collected prior to IMP discontinuation. Additional details will be provided in the SAP.

- “2-dimensional tipping point” multiple imputation will be performed similar to above, the shifts to the distribution will apply to both placebo and active arms, to represent different degrees of effect loss. This analysis will utilize only data collected prior to IMP discontinuation. Additional details will be provided in the SAP.
- The primary analysis for the 2 endpoints will be repeated when missing data will be imputed using a mixed approach of last observation carried forward (LOCF) and baseline observation carried forward (BOCF) as follows: BOCF will be used for patients who had a positive change from baseline at the time of study or IMP discontinuation (ie, a change of 0), while LOCF will be used for patients that have negative change from baseline. In this imputation method, the imputed value is the lower between LOCF and BOCF for each patient. No adjustments will be made to other patients.
- For the first primary endpoint of change from baseline in the weekly average of percent predicted trough morning FEV₁ over the 12-week treatment period, analysis will be performed using a mixed model for repeated measures (MMRM). This analysis will not use retrieved dropout data. This analysis represents a MAR assumption.

9.5.4.3. Secondary Efficacy Analysis

For all secondary endpoints, analyses will be performed using the ITT analysis set and will not include retrieved dropout data in the analysis.

Analysis of change from baseline in weekly average of daily trough morning PEF, total daily use of albuterol/salbutamol, total daily asthma symptom score, and C-ACT score over the 12-week treatment period will be analyzed using an MMRM analysis with effects due to baseline, sex, age, (pooled) investigational center, previous therapy (ICS or NCS), treatment, time, and time-by-treatment interaction. For all of these endpoints, the MMRM will use only observations collected until IMP discontinuation.

The time to first onset of effect, defined as the first decrease from baseline in daily rescue medication use, will be analyzed using a log-rank test. Median and mean time to first onset of effect and associated 95% CIs will be estimated. Time to first onset of effect will also be displayed graphically with a Kaplan-Meier figure.

The proportion of patients who discontinued from IMP for asthma exacerbation during the 12-week treatment period will be analyzed using a logistic regression model with effects due to previous therapy (ICS or NCS) and treatment. These patients will be considered as nonresponders in this analysis.

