6.2. Secondary Efficacy Measures

The secondary efficacy measures and time points for this study are as follows:

- PEF will be measured by the patient (with assistance from the parents/legal guardians/caregivers, as needed) with a handheld device in the morning and evening before administration of IMP or rescue medications. The time points for assessment of PEF as a secondary efficacy endpoint are specifically the morning (predose and pre-rescue bronchodilator) evaluation over the 12-week treatment period.
- The total daily (24-hour) use of albuterol/salbutamol inhalation aerosol will be calculated based on information recorded in the daily patient diary built into the handheld device by the patient (with assistance from the parents/legal guardians/caregivers, as needed) over weeks 1 through 12.
- Daytime and nighttime asthma symptom scores will be recorded in the daily patient diary built into the handheld device by the patient (with assistance from the parents/legal guardians/caregivers, as needed) over weeks 1 through 12.
- The C-ACT will be completed at weeks 4, 8, and 12 and at the IMPDV.
- The time to first onset of effect, defined as the first decrease from baseline in daily rescue medication use, will be calculated based on information recorded in the daily patient diary built into the handheld device by the patient (with assistance from the parents/legal guardians/caregivers, as needed).
- The proportion of patients who discontinued from IMP for asthma exacerbation during the 12-week treatment period will be evaluated over the 12-week treatment period.

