6.3.2. Analysis Methods for Secondary Efficacy Variables

The analysis of the secondary efficacy variables will be performed on the ITT analysis set without retrieved dropout data.

6.3.2.1. Change from Baseline in the Weekly Average of Daily Trough Morning (Predose and Prerescue Bronchodilator) Peak Expiratory Flow (PEF) Over the 12-week Treatment Period

The analysis of change from baseline in the weekly average of daily morning (predose and pre-rescue bronchodilator) PEF over the 12-week treatment period will be performed using an MMRM with effects due to baseline weekly average of daily morning PEF, sex, age, (pooled) investigational center, previous therapy (ICS or NCS), week, treatment, and week-by-treatment interaction. No explicit structure will be assumed for the covariance among the repeated measures. However, if there is a convergence problem with unstructured covariance, then a compound symmetry covariance structure will be assumed.

6.3.2.2. Change from Baseline in the Weekly Average of Total Daily (24-hour) use of Albuterol/Salbutamol Inhalation Aerosol (Number of Inhalations) Over Weeks 1 Through 12

The change from baseline in the weekly average of total daily (24-hour) use of albuterol/salbutamol inhalation aerosol (number of inhalations) over weeks 1 through 12 will be analyzed using an MMRM with effects due to baseline value, sex, age, (pooled) investigational center, previous therapy (ICS or NCS), week, treatment, and week-by-treatment interaction. No explicit structure will be assumed for the covariance among the repeated measures. However, if there is a convergence problem with unstructured covariance, then a compound symmetry covariance structure will be assumed.

6.3.2.3. **Change from Baseline in the Weekly Average of the Total Daily Asthma Symptom Score (Defined as the Average of the Daytime and Nighttime Scores) Over Weeks 1 Through 12**

The change from baseline in the weekly average of the total daily asthma symptom scores over weeks 1 through 12 will be analyzed using an MMRM with effects due to baseline score, sex, age, (pooled) investigational center, previous therapy (ICS or NCS), week, treatment, and week-by-treatment interaction. No explicit structure will be assumed for the covariance among the repeated measures. However, if there is a convergence problem with unstructured covariance, then a compound symmetry covariance structure will be assumed.

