7.2. Multiple Comparisons for the Secondary Analysis

If the p-value is less than 0.05 for the 3 inferential comparisons in the primary analysis, inferential testing will be extended to the secondary analysis.

Testing of secondary efficacy variables for the study drugs will be performed in the sequential manner described in [Table 8](#) (Fp MDPI) and [Table 9](#) (FS MDPI).

Treatment comparisons will begin with the change from baseline in weekly average of daily trough morning PEF (first secondary endpoint) with Fp MDPI 50 mcg versus placebo for

Fp MDPI, or FS MDPI 50/12.5 mcg versus placebo for FS MDPI. If the resulting p-value is less than 0.05, the next comparison(s) of interest will be made according to the direction of the arrows. To the right, this will be the same endpoint to compare Fp MDPI 25 mcg versus placebo (Fp MDPI), or FS MDPI 50/12.5 mcg versus Fp MDPI 25 mcg (FS MDPI). To the next endpoint, this will be the change from baseline in the weekly average of the total daily (24-hour) use of albuterol/salbutamol inhalation aerosol (second secondary endpoint) at the Fp MDPI 50 mcg versus placebo (Fp MDPI), or FS MDPI 50/12.5 mcg versus placebo (FS MDPI).

This process will continue testing sequentially through the next study drug/strength for each variable and at a given strength through the order presented in [Table 8](#) and [Table 9](#) until either all comparisons of interest are made, or until the point at which the resulting p-value for a comparison is greater than 0.05. At the point where the p-value is greater than 0.05, no further comparisons of either that strength or that measure can be made. This procedure allows for control of the Type I error for comparisons at a particular study drug/strength over the 6 secondary endpoints, as well as comparisons over study drugs/strengths within a particular endpoint. However, it does not control the overall Type I error, nominal p-value will be reported.

No multiplicity adjustment will be made for other efficacy analyses.

Table 8: Sequence of Testing Secondary Endpoints for Fp MDPI

Secondary Endpoint	Hypothesis Testing	
	Fp MDPI 50 mcg vs. Placebo	Fp MDPI 25 mcg vs. Placebo
[A] Change from baseline in weekly average of daily trough morning PEF over the 12-week treatment period	↓ →	↓
[B] Change from baseline in the weekly average of total daily (24-hour) use of albuterol /salbutamol inhalation aerosol (number of inhalations) over weeks 1 through 12	↓ →	↓

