APPENDIX E. SENSITIVITY ANALYSIS: MMRM

Similar to the primary estimand, retrieved dropout data will not be used in this sensitivity analysis. Missing data are not implicitly imputed in the MMRM analysis; however, all nonmissing data for a patient will be used within the analysis to estimate the time-averaged difference between treatment groups over 12 weeks. This analysis represents a MAR assumption.

Change from Baseline in Weekly Average of the Percent Predicted Trough Morning FEV₁ Over Week 12:

The sensitivity analysis will be performed using a MMRM with effects due to baseline FEV₁, sex, age, (pooled) center, previous therapy (ICS or NCS), week, treatment, and week-by-treatment interaction. No explicit structure will be assumed for the covariance among the repeated measures. However, if there is a convergence problem with unstructured covariance, then a compound symmetry covariance structure will be assumed.

The estimated treatment means and treatment mean difference derived from the MMRM analysis between each treatment will be presented together with 2-sided 95% CI for the means and the mean difference with corresponding p-value. An example of the SAS codes is as followed:

```
proc mixed data=fev1cfb;
    class usubjid sex center therapy week trt;
    model cfev=bfev sex age center therapy week trt week*trt
        /ddfm=KR;
    repeated week / type=un sub=usubjid(trt) r;
        ***repeated week / type=cs sub=usubjid(trt) r;
        ***If type=un fails to converge;

    /* Compare active Fp treatment to Placebo over 12 weeks */
    estimate `Fp 25 mcg BID vs Placebo'      trt  1 0 0 -1 /cl;
    estimate `Fp 50 mcg BID vs Placebo'      trt  0 1 0 -1 /cl;

    lsmeans trt week*trt / diff cl;
    ods output Estimates=Est LSMeans=lsmeans Diffs=Diffs;

run;
where: cfev and bfev denote change from baseline and baseline value of
percent predicted FEV1 respectively; week = 1, 2, 3, 4, 5, 6, 7, 8, 9,
10, 11, 12 representing weeks 1 to 12 respectively; and trt is the
treatment for the primary analysis:

    A = Fp MDPI 25 mcg BID
    B = Fp MDPI 50 mcg BID
```

C = FS MDPI 50/12.5 mcg BID
D = Placebo

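### The MMRMs fit one baseline slope across all time points; a baseline-by-week term is a nearly free guard against a possible small loss of precision

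*Protocol*

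**What the plan says.** Protocol 9.5.4.3 specifies, for morning PEF (A), rescue use (B), symptom score (C) and C-ACT (D), an "MMRM analysis with effects due to baseline, sex, age, (pooled) investigational center, previous therapy (ICS or NCS), treatment, time, and time-by-treatment interaction". SAP 6.3.2.1 to 6.3.2.4 repeat the list: baseline, the other covariates, and then "previous therapy (ICS or NCS), week, treatment, and week-by-treatment interaction". Only treatment is crossed with week. SAP 6.4.2.1 (rescue use at weeks 4, 8 and 12) and 6.4.2.6 (evening PEF) use the same terms. So does the analysis code in Appendices B, C and E; Appendix E has "model cfev=bfev sex age center therapy week trt week*trt".

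On covariance, SAP 6.3.2 says "No explicit structure will be assumed for the covariance among the repeated measures". If that does not converge, "then a compound symmetry covariance structure will be assumed".

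A to C have 12 weekly values. D does not: Protocol 6.2 states "The C-ACT will be completed at weeks 4, 8, and 12 and at the IMPDV". SAP 7.2 tests A to D over the treatment period, so no single-week estimate enters the secondary testing sequence.

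**The concern.** For A to C, SAP 4.2 defines baseline as the average of the 7 days before randomization, taken during placebo run-in with controllers stopped. Week 1 adjoins that window and week 12 does not, so the correlation with baseline may well fall over follow-up. In that case the true slope differs by week and one slope cannot fit all weeks. With unstructured covariance, generalized least squares weights the common slope toward the early weeks, where residual variance is smaller. Later weeks, and to a lesser degree the 12-week mean, are then over-adjusted, and the excess goes into the error.

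The SAP does not impose one slope everywhere. The imputation regressions in Appendices A, B and C include baseline in a separate regression for each week, so its coefficient can differ by week. Appendices B and C then analyse those imputed data with a single slope.

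At stake is some power. Under SAP 7.2 a non-significant secondary result stops testing for that strength or that measure.

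**Working it through.** **What can be reproduced.** The plan states no power, variance or baseline correlation for A to D. Its 80% power belongs to the week-12 primary comparisons (Protocol 9.1). If the quoted 6.5 and 5 are taken as treatment differences:

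- FS versus Fp: 2 × (1.960 + 0.842)² × (22/6.5)² ≈ 180 per group.
- Fp versus placebo: 2 × (1.960 + 0.842)² × (17/5)² ≈ 182 per group.
- 181/0.88 ≈ 206 randomized per group.

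This agrees with the stated 181 and 206 but says nothing about A to D. The 80% is used below only as an illustration.

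**Formula (complete data).** Let βⱼ be the true baseline slope at week j, S the residual covariance given baseline, and baseline variance 1.

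- Common slope: b = 1′S⁻¹β / 1′S⁻¹1.
- Variance ratio for the 12-week mean, without versus with baseline-by-week: 1 + (mean β − b)² / Var(mean residual).
- Variance ratio for one week: 1 + (βⱼ − b)² / Sⱼⱼ.

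Equal slopes give b = β and a ratio of exactly 1.

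**Assumptions (none from the documents).** Unit-variance series with random intercept 30-50%, AR(1) 0.7-0.9 per week, and independent weekly noise of 0, 10 or 20%. The baseline correlation then falls from 0.65-0.95 at week 1 to 0.31-0.64 at week 12.

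**One setting in full.** Random intercept 40%, AR(1) 0.8, noise 10%.

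- Week-1 correlation: 0.4 + 0.5 × 0.8 = 0.80.
- Week-12 correlation: 0.4 + 0.5 × 0.8¹² = 0.434.
- Mean slope 0.555; fitted common slope 0.674; variance of the mean residual 0.346.
- 12-week mean: 1 + (0.555 − 0.674)²/0.346 ≈ 1.041.
- Week 12 (residual variance 0.811): 1 + (0.434 − 0.674)²/0.811 ≈ 1.071.

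**All settings.** Power is Φ(2.802/√ratio − 1.960), starting from a nominal 80%.

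| Weekly noise | 12-week mean, A to C | Power | Week 12 alone |
|---|---|---|---|
| 20% | +0.7 to +2.1% | 79.2-79.7% | +1.3 to +5.3% |
| 10% | +2.2 to +5.1% | 78.0-79.2% | +3.2 to +10.0% |
| 0% | +6.2 to +13.1% | 75.0-77.6% | +7.2 to +19.7% |

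The fitted slope exceeded the mean slope in every setting, which is the direction expected.

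**C-ACT.** The same settings at weeks 4, 8 and 12 give +0.0 to +1.0% for the mean and +0.1 to +4.7% at week 12.

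**Rescue use at weeks 4, 8 and 12.** The week-12 column assumes that all 12 weeks are fitted. If SAP 6.4.2.1 fits only those three weeks, the three-visit range applies.

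**Differential dropout.** A simulation used 206 per arm, 12 weeks and missing-at-random dropout of about 18% versus 5%, with 120 replicates for each falling-correlation setting. The two models' 12-week means differed by 0.004-0.007 SD and their week-12 estimates by 0.012-0.021 SD. Coverage for the 12-week mean agreed within 1 point (Monte Carlo error 2-3 points).

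**The case against.** A main-effect baseline is a legitimate prespecified choice, and much of the case for leaving it alone stands.

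- A reader might infer that the adjustment is wrong for later weeks and that precision is certainly lost. The documents do not support this. Nothing in them shows the slope changing over the weeks, and equal slopes cost nothing.
- A reader might take 13% more variance, or power near 75%, as typical. That end needs zero independent weekly noise. Protocol 9.1 and SAP 2.4 describe inconsistent handheld FEV₁ readings and poor-effort alerts, and PEF comes from the same device.
- A reader might apply the week-12 figure, or the 12-week range, to all of A to D. The sequence tests effects over the period, and C-ACT has only three visits. C-ACT could lose more only if its correlation fell steeply between week 4 and week 12: about 1-5.5% for falls such as 0.8 to 0.5.
- Under the compound-symmetry fallback with complete data, the common slope equals the mean slope and the 12-week mean loses nothing.
- Secondary testing opens only after all three primary comparisons succeed. SAP 7.2 itself says that overall Type I error is not controlled there. The primary week-12 ANCOVA is unaffected.

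These points limit the size and the severity. They do not give a reason to leave the term out.

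**Conclusion.** The omission is real and runs through every MMRM in the plan. Its consequence is conditional and probably small. If the baseline relation weakens over follow-up, the variance of the 12-week mean for A to C is about 0-5% larger, or 0-2 points at a nominal 80% power. C-ACT loses about 0-1%. Week-specific estimates may lose about 1-10%, or up to 20% without weekly noise; the rescue-use estimates in SAP 6.4.2.1 are the main case. All of these sizes rest on assumed correlations.

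It would go too far to read this as invalidating the A to D tests. With complete data, randomization keeps the contrasts unbiased whatever slope is fitted. Under the simulated dropout the 12-week means differed by only 2-3% of the assumed 0.22 SD effect. This is a free improvement of minor severity.

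**What to change.** Before database lock, add baseline-by-week to each MMRM in SAP 6.3.2.1 to 6.3.2.3, 6.4.2.1 and 6.4.2.6 and in Appendices B, C and E, and baseline-by-visit for C-ACT in 6.3.2.4. In Appendix E, for example:

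`model cfev = bfev bfev*week sex age center therapy week trt week*trt`

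In Appendices B and C the term is `base*visit`. Bring Protocol 9.5.4.3 into line, or list the change in SAP section 11. SAP 6.4.2.1 should also say whether it fits all 12 weeks or only weeks 4, 8 and 12.

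The cost is one model term per analysis: 11 degrees of freedom for 12 weeks, or 2 for three visits, among about 824 patients. No new data are needed. SAP 2.5.2 requires amendments to be approved before database lock; added later, the term would be post hoc.
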